- (2) **Control Conditions Hypothesis:** We hypothesize significant differences in signal intensity across the three different epoch conditions—TM, passive-attending and mental-counting. Specifically, de-excitation will be maximum for TM, then passive-attending, and lastly, mental-counting.

Aim 2: Maximum De-excitation Meditation Substate. We predict that event-related (er-fMRI) and state-related (sr-fMRI) analytic procedures will yield distinct spatial and temporal patterns of BOLD intensity that characterize the maximum de-excitation substate associated with spontaneous breath-quiescent periods (SBQ, breath period > 10 sec). We will test five hypotheses in this experiment.

- (3) **IBH-Blood Gas Hypothesis:** Using event-related-fMRI, we hypothesize moderate changes in blood gas changes will be detected during Intentional Breath-Holding (IBH), and blood gas levels will be significantly correlated with changes in BOLD signal intensity, consistent with published findings.
- (4) **SBQ-Blood Gas Hypothesis:** Using event-related-fMRI, we hypothesize small changes in blood gas changes will be detected during Spontaneous Breath Quiescence (SBQ), and blood gas levels will not be significantly correlated with changes in BOLD signal intensity.
- (5) **SBQ-IBH Hypothesis:** Using event-related-fMRI, we hypothesize that specific spatiotemporal patterns of BOLD signal will be associated with onset of SBQ, and will differ from IBH control periods in terms of reduced BOLD signal of the anterior cingulate cortex and brainstem during SBQ.
- (6) **SBQ-Controls Hypothesis:** Using state-related-fMRI, we hypothesize that BOLD signal intensity patterns during SBQ periods will differ from two control conditions—IBH periods, and eyes-closed periods (as defined in Aim 1, either passive-attending or mental-counting).
- (7) **SBQ-Non-SBQ Hypothesis:** Using state-related-fMRI, we hypothesize that BOLD signal intensity patterns during SBQ periods will differ from the scans during non-SBQ periods during meditation.

B. BACKGROUND AND SIGNIFICANCE

B.1. Need for Basic Neuroscience Research on Mechanisms of CAM Modalities.

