D.6.1.1 IBH-Blood Gas Hypothesis. Using event-related-fMRI, we hypothesize moderate changes in blood gas changes will be detected during Intentional Breath-Holding (IBH), and blood gas levels will be significantly correlated with changes in BOLD signal intensity, consistent with published findings.

D.6.1.2 SBQ-Blood Gas Hypothesis. Using event-related-fMRI, we hypothesize small changes in blood gas changes will be detected during Spontaneous Breath Quiescence (SBQ), and blood gas levels will not be significantly correlated with changes in BOLD signal intensity.

D.6.1.3. SBQ-IBH Hypothesis. Using event-related-fMRI, we hypothesize that specific spatiotemporal patterns of BOLD signal will be associated with onset of Spontaneous Breath Quiescence (SBQ), and will

differ from IBH control periods as marked, in particular, by reduced BOLD signal of the anterior cingulate cortex and brainstem during SBQ.

D.6.1.4. SBQ-Controls Hypothesis. Using state-related-fMRI, we hypothesize that BOLD signal intensity patterns during SBQ periods will differ from two control conditions—IBH periods, and eyes-closed periods (as defined in Aim 1, either passive-attending or mental-counting).

D.6.1.5. SBQ-Non-SBQ Hypothesis: Using state-related-fMRI, we hypothesize that BOLD signal intensity patterns during SBQ periods will differ from the scans during non-SBQ periods during meditation.

D.6.2. Issues.

The second phase of the grant will systematically explore neural patterns underlying the second principal substate during TM practice—periods of SBQ with durations of 10 to 40 sec—signifying the maximum de-excited state of TM practice. A study of breath-quietness raises a number of possible confounds.

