Research on a various forms of respiratory challenge, e.g., CO₂ inhalation, hyperventilation, breath-holding, etc., versus normal breathing have reported reproducible networks of forebrain and brainstem activation based on significant and specific changes in BOLD signal intensity. Furthermore, these patterns are discernible even with the considerable confounds of respiratory-induced variability of head and brainstem position, as well as wide variations in blood gas values. In contrast, the spontaneous breath-quietness periods during the TM practice occur under relaxed, non-stressful conditions, with the onset, persistence and offset of spontaneous breath-quietness not dependent upon volitional or intentional control or even awareness of the individual. Because of the restful state of the meditator, there is also minimal head movement artifact. **In conclusion, we anticipate that the potentially small, independent effects of respiratory-mediated BOLD signal changes will not significantly confound the data collected during spontaneous breath-quietness substate of the TM technique.**

D.6.2.2 Effectsof cessation of mechanical respiratory activity. Intentional breath-holding will be used to clarify the impact of breath-quietness on brain function and MRI signal intensity. These breath-holding periods will allow comparison of CO₂ variation and control for effects arising from cessation of mechanical respiratory activity. Because breath-quietness occurs spontaneously during TM practice, the cycling protocol cannot be used requiring the recording of images during a “self-paced” protocol, in which no instructions are given and TM is uninterrupted. This non-cycling design will produce a 5 min time-series of scans that will have reoccurring periods of spontaneous breath-quietness embedded in it. In addition, analytical approaches will be used that are capable of marking desired scans and comparing the variability of signal intensity in the time series. Event-related and state-related fMRI methodologies will be used to analyze the continuous sequence of scans [personal communication, [name] and [name], 2001][[name], 1998 #4780;[name], 1998 #4781;McCarthy, 1999 #5209;Schacter, 1997 #5391].

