The BOLD signal and physiological measures will be collected during four runs of 12 minutes duration each. Each 12 min run comprises three periods: 5 min uninterrupted meditation, 5 min structured breath-holding, and 2 mins non-task, eyes-closed (EC) control. The meditation period are free running with no interruptions from experimenters. During the meditation period we expect 3-5 SBQ periods. The breath-holding periods are structured by duplicating the previous SBQ pattern by voice command from experimenter, the onset and offset of IBH corresponding to SBQs time frame for each subject. The non-task control period will be determined from the outcome of experiment 1 (Aim 1), and either be passive-attending or mental-counting. The physiological measures will include respiration and transcutaneous CO₂ measurements. Four runs will take 48 minutes, or about 1 hr due to 30 rest periods between conditions. Therefore, each fMRI session will last about 90 minutes per subject.

D.6.4. Event-related fMRI analysis (Hypotheses 1-3).

Er-fMRI methodologies will be used to probe brain mechanisms during the onset of two conditions, during SBQ and IBH periods. The scans will be aligned relative to the onset of either SBQ or IBH during the four runs to permit signal averaging: 4 images before (12 secs) and 4 images after onset (12 secs). A TM meditator, selected in our screening protocol, may exhibit 25-30 spontaneous breath-quiet periods in a 30-min TM session [9, 20-22]. We estimate 12-20 periods will occur in our four meditation periods.

Images from individual runs will first be normalized to correct for the range of intra- and inter-subject signal intensity and temporal drift [171]. Specifically, normalization will involve: (1) scaling of signal intensity to a fixed value of 1000; (2) linear slope removal in a voxel-by-voxel basis; (3) spatial filtering with a one-voxel radius Hanning filter, and; (4) removal of the mean signal intensity on a voxel-by-voxel basis. The normalized fMRI images will then be aligned relative to the onset either SBQ or IBH periods. These images will be averaged within each subject. The mean image for each subject will be transformed into stereotaxic atlas space [208] using the highest point of the mid-sagittal plane and the anterior and posterior commissures. The atlas-transformed matrices will then be averaged across subjects.

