Statistical parameter maps will be constructed using sets of pre-constructed hemodynamic curves. Cohen's hemodynamic model, often used in fMRI experimental analysis, was derived from stimulation of the visual cortex [170]. Hence, there is no reason to suspect it is the best response function to apply to this task (meditation) or to other brain areas (subcortical nuclei). Therefore, new response models will be constructed by systematically varying, initially, the onset delay (lags) of Cohen's standard hemodynamic response model. Other parameters besides onset could also be varied, e.g., shape of curve. Sequential application of each model will display the inherent temporal and spatial dynamics of the hemodynamic response to the onset of the spontaneous breath-quiet substate. Each model will generate a different map of the brain dynamics. For example, short versus mid or long lags could be reasonably expected to produce different anatomical patterns [171]. On the other hand, the brain pattern may remain similar, but the signal intensity of each brain area may vary. Models derived from both conditions can be compared to determine statistical significance of the two brain states. Specifically, we will use MANOVA to compare onset, latency and peak signal intensity for different ROIs for the two conditions. We expect, in general, that the statistical parameter maps for intentional breath-holding will depict a diffuse, non-localized distribution of activation in contrast to localized patterns of activation during spontaneous breath-quiet. Hypothesis 1 & 2 will use a correlational analysis to test association between er-fMRI BOLD signal intensity and blood gas levels.

D.6.4.1 Blood Gases and IBH. O₂ and CO₂ levels will be correlated with er-fMRI BOLD signal intensity during the 6 scans (18 s) preceding and the 4 scans (12 s) following the onset of IBH. Data will be analyzed with a Pearson correlation to help distinguish blood gas-dependent vs. neural-dependent BOLD changes.

- We expect significant correlations between CO₂, but not O₂, with BOLD signal during IBH.

D.6.4.2. Blood Gases and SBQ. O₂ and CO₂ levels will be correlated with er-fMRI BOLD signal intensity during the 6 scans (18 s) preceding and the 4 scans (12 s) following the onset of spontaneous breath-quiet. Data will be analyzed with a Pearson correlation help distinguish blood gas-dependent versus neural-dependent BOLD changes.

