- We expect minor blood gas changes and hence, few significant correlations between CO₂, with BOLD signal during spontaneous breath-quietness.

D.6.4.3. Neuroimages during SBQ and IBH. Er-fMRI will be compared between IBH and SBQ periods, using a repeated measures MANOVA.

- We expect main effects for brain areas. Animal hypercapnia [209] and human breath-holding [157, 203, 210, 211] studies indicate that hypercapnic conditions are associated with global increases in most cortical and subcortical grey matter blood flow. Thus, we expect region-independent, nonspecific activation in all areas during IBH. In contrast, we expect region-dependent, specific activation or deactivation of BOLD signal intensity during SBQ.
- We expect main effects for the repeated measures, indicating significant differences in signal intensity across time.
- We expect no significant interactions.

D.6.5. State-related fMRI analysis (Hypotheses 4-5).

Sr-fMRI methodologies will be used to probe brain mechanisms during SBQ, IBH, and control periods. In the previous three analyses, we identified brain areas that displayed significant time-locked relation to the onset of both IBH and SBQ. A complementary approach to identification of brainstate changes is the use of state-related methodology. This method divides the time-series into condition-specific bins for comparison. Scans collected in Expt. 2 will be categorized into six bins: before and during either IBH, SBQ or equal-length periods during eyes-close (EC) control. Scans assigned to each bin will be compared by multiple linear regression, correcting for differences in blood gas levels across the three conditions.

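### The breath-hold and SBQ blood-gas hypotheses each claim a size of gas change, but the only analysis assigned to them is a Pearson correlation with BOLD, which does not estimate that size

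*Protocol*

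**What the plan says.** The two hypotheses are numbered 3 and 4 in the Specific Aims, and D.6.4 calls them 1 and 2. Each has two parts.

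- **Size of the gas change.** For IBH (D.6.1.1): "we hypothesize moderate changes in blood gas changes will be detected during Intentional Breath-Holding (IBH"). For SBQ (D.6.1.2): "we hypothesize small changes in blood gas changes will be detected during Spontaneous Breath Quiescence (SBQ").
- **Link with BOLD.** A significant correlation is predicted in IBH. In SBQ, "blood gas levels will not be significantly correlated with changes in BOLD signal intensity".

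The analysis is assigned in D.6.4: "Hypothesis 1 & 2 will use a correlational analysis to test association between er-fMRI BOLD signal intensity and blood gas levels". D.6.4.1 gives the method for IBH: "Data will be analyzed with a Pearson correlation to help distinguish blood gas-dependent vs. neural-dependent BOLD changes". D.6.4.2 repeats it for SBQ and closes with an expectation: "We expect minor blood gas changes and hence, few significant correlations".

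D.6.2.1 concludes in advance that "potentially small, independent effects of respiratory-mediated BOLD signal changes will not significantly confound the data" for the SBQ substate. D.6.2.2 says the breath-holds will make a comparison of CO2 variation possible, but gives no analysis for it. D.6.3 supplies the matching: "The breath-holding periods are structured by duplicating the previous SBQ pattern by voice command from experimenter", with onset and offset following each subject's own SBQs.

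**The concern.** The first part of each hypothesis concerns how much the gas moves, and the only statistic assigned concerns how closely gas and BOLD move together. The terms moderate, small and minor are given no estimate, contrast or bound. The D.6.4.2 expectation takes the small change as its premise and the scarcity of correlations as its consequence. A non-significant coefficient could therefore be read as support for a premise that was never examined.

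The protocol itself gives reason to examine it. D.6.2.1 acknowledges that quiet breathing can shift CO2 appreciably. D.6.3 expects CO2 to rise during the slow inhalation that may make up SBQ. D.6.5.2 attributes part of a predicted condition effect to possibly higher CO2 in IBH. At stake is whether the trial can report on half of two numbered hypotheses, and how safely the direct SBQ-IBH map comparison can be interpreted.

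**Working it through.** The protocol gives no power, effect size or standard deviation for these hypotheses, so there is no figure of its own to reproduce.

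**1. Every planned use of gas data**

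| Place | Role of gas |
|---|---|
| D.2.2, D.6.2.1 | covariable in multiple regression |
| D.6.4.1, D.6.4.2 | correlated with BOLD |
| D.6.4.3 (SBQ against IBH, event-related MANOVA) | none named |
| D.6.5, D.6.5.1 (state-related regression) | covariable |
| D.6.2.2 | comparison mentioned, no analysis given |

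The ANOVA and MANOVA outcomes in D.6.4.3 and D.6.5 are BOLD measures or Z-statistics. Gas is never the outcome.

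**2. What Pearson r says about size**

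In an artificial 10-point series with BOLD held fixed, multiplying CO2 by 1, 0.1 and 5 left r at 0.92 each time. The before-to-during change was 2.48, 0.25 and 12.4.

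Holding BOLD fixed is the extreme case. If BOLD follows CO2 with slope b and fixed noise SD s, then r = b·SD(CO2) / √(b²·SD(CO2)² + s²). Here r does fall as the gas range shrinks. But halving SD(CO2), halving b and doubling s all give the same r. A low r can therefore reflect a small gas change, a weak BOLD response or noisy BOLD, and r alone cannot separate them.

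**3. What a non-significant r shows**

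Inputs: 6 scans before and 4 after onset (D.6.4.1-2), so n = 10. Assumptions: two-sided 5%, scans independent (optimistic for a time series).

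Critical |r| = t / √(n − 2 + t²) with t(0.975, 8 df) = 2.306, giving 2.306 / √(8 + 5.318) = 0.632.

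Simulated power:

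| True r | Power |
|---|---|
| 0.3 | 13% |
| 0.5 | 33% |
| 0.6 | 49% |
| 0.7 | 68% |

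Pooling events would raise the power, but would still not make r an estimate of gas change.

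**4. What a direct estimate would offer**

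- *Pairs.* Four runs with 3-5 SBQs each (D.6.3) give 4 × 3 = 12 to 4 × 5 = 20 per session. With 10 subjects (D.2.4, D.4.3) and one session each, that is 120-200. The Year 2 timeline (D.3) lists 20 sessions. If that means 20 / 10 = 2 per subject, the total is 240-400.
- *Precision.* 95% half-width = t(0.975, 9 df) / √10 = 2.262 / 3.162 = 0.715, or about 0.72 SD of the subject-level paired differences.
- *Power.* A paired t-test with n = 10 (noncentral t, two-sided 5%) has 29% power at a standardised difference of 0.5 and 62% at 0.8. It reaches 80% at about 1.00 and 90% at about 1.15.

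No CO2 standard deviation is given, so none of this converts to mmHg.

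**The case against.** A reader might infer that confounding of Aim 2 by gas is left wholly open, or that it turns on this untested size. The documents do not support that. What matters for confounding is whether gas explains BOLD, and the plan addresses this. Physiological series are covariables in the standard regression (D.2.2), gas measures are covariables for the breath-quietness work (D.6.2.1), and the state-related regression adjusts for O2 and CO2 (D.6.5, D.6.5.1).

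A reader might also infer that equal CO2 rises in SBQ and IBH would cause SBQ maps to be misread as neural. For the direct contrast the reverse is nearer the truth. With duration-matched breath-holds and the additive effects assumed in D.6.3, equal rises would tend to cancel. Unequal rises, which the protocol predicts, are the threat.

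Three further points carry weight.

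- Expecting fewer correlations when the gas range is narrow is coherent reasoning, as step 2 shows. It does not run backwards from a null correlation to a small change.
- D.6.2.2 does declare a CO2 comparison, and its details could sit in an analysis plan. However, D.6.4 names the test for these two hypotheses, and that test leaves out half of each.
- This is an exploratory grant, so a formal test may be more than is needed. An estimate with an interval suits exploratory work.

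**Conclusion.** The concern holds in a limited form. The size part of both blood-gas hypotheses has no planned analysis, and the statistic assigned to them does not estimate it. A non-significant SBQ correlation would not establish a small gas change: with 10 independent scans, a true correlation of 0.5 would be missed about two times in three.

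Confounding is partly handled by covariate adjustment. The exposed place is D.6.4.3, where SBQ and IBH are compared directly and neither that section nor the normalise-align-average sequence in D.6.4 names a gas adjustment. An unequal CO2 change between the two conditions would matter most there.

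The power figures assume a two-sided 5% level and independent scans. The precision figures assume 10 subjects analysed at subject level, so extra pairs help only by reducing within-subject noise. This is a worthwhile repair to the analysis and does not invalidate Aim 2.

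**What to change.** In D.6.4.1 and D.6.4.2:

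1. Define for each event the change in CO2, and in O2, from before the pause to during or just after it.
2. Compare each SBQ with its duration-matched breath-hold in a within-subject paired model, with pairs nested in subject.
3. Report the mean change in SBQ, the mean change in IBH and their difference, each with a 95% confidence interval.
4. State that a non-significant correlation will not be taken as evidence of a small change. Call the SBQ change small only if its upper confidence limit lies below a bound that the sponsor fixes before the data are seen.
5. State whether the D.6.4.3 comparison adjusts for gas.

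Reconcile D.6.2.1, which plans end-tidal CO2 by nasal cannula, with D.6.3, which lists transcutaneous CO2. The change must be defined on the measure actually recorded, and a breath-by-breath definition would work only with the former.

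The cost is a few lines of text and slight extra analysis of gas data the trial already plans to collect.

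### The onset-locked windows in D.6.4 make no allowance for a preceding breath pause, so at random SBQ timing some pre-onset scans carry the previous event

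*Protocol*

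**What the plan says.** Each Experiment 2 run comprises "5 min uninterrupted meditation, 5 min structured breath-holding, and 2 mins non-task, eyes-closed (EC) control" (D.6.3). On event frequency the same section states: "During the meditation period we expect 3-5 SBQ periods". D.6.2 describes "periods of SBQ with durations of 10 to 40 sec". IBH is prompted so that its onsets and offsets reproduce the subject's preceding SBQ pattern.

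Two onset-locked windows follow:

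- **D.6.4, signal averaging:** "4 images before (12 secs) and 4 images after onset (12 secs". Aligned images are averaged within subject, then across subjects. Onset, latency and peak are compared between SBQ and IBH by MANOVA.
- **D.6.4.1 and D.6.4.2, blood gases:** O2 and CO2 are correlated with BOLD, for IBH "during the 6 scans (18 s) preceding" onset and the 12 s after it, and for SBQ "during the 6 scans (18 s) preceding and the 4 scans (12 s) following the onset of spontaneous breath-quiet". On the statistic: "Data will be analyzed with a Pearson correlation help distinguish blood gas-dependent versus neural-dependent BOLD changes".

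D.6.4 to D.6.4.3 set no minimum gap between events, give no rule for closely spaced onsets and describe no overlap correction.

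**The concern.** Onset-locked averaging treats the scans before an onset as free of the event. SBQs are self-paced, so the gap between one pause and the next varies. When it is shorter than the window, the pre-onset scans hold BOLD signal and CO2 from the previous pause.

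For the averages, this raises or lowers the pre-onset level towards the event level and blurs the onset response from which onset, latency and peak are taken. For the correlations, it mixes recovery from one pause with the start of the next. Those correlations carry the IBH and SBQ blood-gas hypotheses (Hypotheses 3 and 4 in the Specific Aims, 1 and 2 in the D.6.4 numbering). The amount depends on each subject's SBQ rate and length, so it also adds between-subject variation in a study of 10 subjects.

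**Working it through.** **Inputs from the protocol.** Period 300 s; n = 3-5 SBQs per period (D.6.3); length L = 10-40 s (D.6.2); window w = 12 s (D.6.4) or 18 s (D.6.4.1-2).

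**The protocol's own figures.** Four periods x 3-5 SBQs = 12-20, as D.6.4 states. D.6.4 also says that a selected meditator "may exhibit 25-30 spontaneous breath-quiet periods in a 30-min TM session". That is one onset per 60-72 s, or about 4.2-5 per 5 min, consistent with the upper part of 3-5.

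**Assumption not in the protocol.** The n events fall at random, without overlapping, in the 300 s. With S = 300 - nL, the chance that less than w seconds precede an onset is 1 - (1 - w/S)^n. This counts the first event of a period, whose window can only reach past the period start. Multiplying by (n - 1)/n leaves the share of onsets whose window contains part of a previous SBQ.

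| n, L | S | 18 s: all short gaps | 18 s: previous SBQ | 12 s: all short gaps | 12 s: previous SBQ |
|---|---|---|---|---|---|
| 3, 10 s | 270 | 1 - 0.813 = 19% | x 2/3 = 12% | 13% | 8% |
| 4, 25 s | 200 | 1 - 0.686 = 31% | x 3/4 = 24% | 22% | 16% |
| 5, 25 s | 175 | 1 - 0.581 = 42% | x 4/5 = 34% | 30% | 24% |
| 5, 40 s | 100 | 1 - 0.371 = 63% | x 4/5 = 50% | 47% | 38% |

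The last row needs every SBQ to last 40 s, so 200 of 300 s are spent in SBQ.

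**Sensitivity to the timing assumption** (18 s, onsets that have a predecessor):

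- Exponential gaps: 1 - exp(-18/90) = 18% for 3 per period and 10 s, up to 1 - exp(-18/20) = 59% for 5 per period and 40 s.
- Moderately regular gaps (gamma shape 2): 6-54%.
- Clustered gaps (gamma shape 0.5): 35-66%.
- Even spacing: 0%. The shortest gap is 60 - 40 = 20 s, above 18 s.

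These shares ignore response lag. If BOLD carries over for 6 s after offset (assumed), the exponential range becomes 1 - exp(-24/90) = 23% to 1 - exp(-24/20) = 70%. In the other direction, D.2.1 gives a TR of 2.2 s while the windows imply 3 s per scan. Six scans at 2.2 s cover 13.2 s, and the share reaching a previous SBQ is then about 9-41%. That mismatch is a separate matter.

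**Effect on the average.** With simulated random placement, a sustained response and about 5-s lag (both assumed), the mean post-minus-pre change in the 12-s window was 90%, 73%, 62% and 40% of its isolated-event value in the four rows. A separate simulation with exponential gaps and another response model fell from about 0.5 in clean onsets to 0.44 (sparsest) and 0.12 (densest) over all onsets.

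**Effect on the correlation.** For a CO2-driven signal, the mean within-event r moved from 0.33 (clean onsets) to 0.31 (all onsets) in the sparsest case, and from 0.30 to 0.29 in the densest. The r pooled over onsets rose from 0.35 to 0.44 and from 0.45 to 0.77. The sign of the distortion depends on how r is formed, which D.6.4.1-2 do not say.

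**The case against.** The strongest reply has four parts.

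1. **The percentages do not follow from the stated rates alone.** This stands. They need random timing, and the protocol gives no distribution of gaps. Even spacing gives none. But SBQs are described as spontaneous and not under volitional control, so nothing supports even spacing either.
2. **The 18-s window is not a subtracted baseline.** This also stands. It feeds a Pearson correlation, so dilution of a pre-to-post change belongs to the 12-s averaging window. D.6.4 does not name a post-minus-pre mean; it compares onset, latency and peak. These are still read from responses in the same contaminated windows.
3. **IBH shares the timing, and D.6.5 uses a convolved regression with gas covariates.** Shared timing gives both conditions the same overlap pattern. It need not give the same size of carry-over, because the protocol expects larger gas changes in IBH. The D.6.5 regression serves the state-related hypotheses and does not repair the averages or correlations in D.6.4.
4. **Event selection may be settled elsewhere.** The text is silent on whether every event is used. It does, however, fix the windows and the averaging, and as written that procedure carries the earlier pause into the pre-onset scans.

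A reader might infer that contamination weakens the expected IBH correlation and favours the expected absence of an SBQ correlation. The documents do not support a direction: an earlier pause moves CO2 and BOLD together and can raise r. Nor can one infer that a CO2-driven change reverses sign. With a 10-s time constant and no added lag, about 66% of the change remained at 4 events of 25 s. With a 5-s lag, the result was 0.02 or -0.38, depending on the model form.

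**Conclusion.** The point holds in limited form and is worth correcting. The D.6.4 windows have no handling of a preceding event, and the protocol's own rates and durations make overlap likely unless spacing is close to even. At random timing, 8-38% of 12-s windows and 12-50% of 18-s windows contain part of a previous SBQ. For 4-5 SBQs of 25 s, the 18-s figure is about 24-34%. The pre-to-post change in the onset-locked average is diluted to roughly 90% in the sparsest case and 40% or less in the densest, under an assumed sustained response with about 5-s lag. The exact values move with the response model. The blood-gas correlations are distorted, with no predictable sign.

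**What to change.** In D.6.4, replace plain onset-locked averaging with one regression per subject that models all SBQ and IBH events of each period jointly. Use event-locked time bins covering the pre-onset window, the event and its recovery, and take onset, latency and peak from that fit. This assumes that responses to successive events add.

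For D.6.4.1 and D.6.4.2, add a sensitivity analysis limited to onsets whose pre-onset window plus response lag is free of the previous event, and drop the matched event in the other condition.

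The cost is a little more analysis work and somewhat wider standard errors where events overlap; the joint fit discards no events. The sensitivity analysis uses fewer onsets. With 18 s plus a 5-s lag, the formula above with w = 23 removes (2/3)(1 - (1 - 23/270)^3) = 16% in the sparsest case and (4/5)(1 - 0.77^5) = 58% in the densest. About 10 of 12 or 8 of 20 SBQ onsets per subject would remain.

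### Hypotheses 3 and 4 are each stated in two incompatible ways, and a shortage of significant correlations cannot show that blood gas has no effect during breath quiescence

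*Protocol*

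**What the plan says.** Hypotheses 3 and 4 appear in Section A (Specific Aims) and again, in the same terms, in D.6.1.1 and D.6.1.2. Section D.6.4 calls them hypotheses 1 and 2 because it numbers within Aim 2, and it names the test: "Hypothesis 1 & 2 will use a correlational analysis to test association between er-fMRI BOLD signal intensity and blood gas levels".

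- **Hypothesis 3 (IBH).** The hypothesis reads "blood gas levels will be significantly correlated with changes in BOLD signal intensity, consistent with published findings". The analysis section D.6.4.1 reads "We expect significant correlations between CO₂, but not O₂, with BOLD signal during IBH".
- **Hypothesis 4 (SBQ).** The hypothesis reads "blood gas levels will not be significantly correlated with changes in BOLD signal intensity". The analysis section D.6.4.2 expects minor gas changes and "few significant correlations between CO₂, with BOLD signal during spontaneous breath-quietness".

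The stated purpose in D.6.4.1 is: "Data will be analyzed with a Pearson correlation to help distinguish blood gas-dependent vs. neural-dependent BOLD changes". The window there is "during the 6 scans (18 s) preceding and the 4 scans (12 s) following the onset of IBH", and D.6.4.2 uses the same window around SBQ onset. Earlier in D.6.4 the images are aligned over a different window: "4 images before (12 secs) and 4 images after onset (12 secs".

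**The concern.** Section D.1 treats the respiratory confound as a central issue for the trial, and D.6.2.1 anticipates that it will not materially affect the SBQ data. Hypotheses 3 and 4 are the pair that tests this expectation most directly: gas should track BOLD when breath is held on purpose and should not when it stops spontaneously.

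Two things weaken that test. First, each hypothesis has one criterion where it is stated and another where it is analysed, so the same result can be reported as support or as refutation. Second, the SBQ side is a prediction of no effect, and the plan would read it from few or no significant correlations. A non-significant test counts against a gas effect only if the test could have found one.

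**Working it through.** **1. The criteria side by side.**
- IBH, O₂ significant and CO₂ not: supports Hypothesis 3; contradicts D.6.4.1 on both gases.
- IBH, both gases significant: supports Hypothesis 3; contradicts D.6.4.1 on O₂.
- SBQ, one CO₂ correlation significant: refutes Hypothesis 4; satisfies D.6.4.2.
- SBQ, O₂ only significant: refutes Hypothesis 4; the D.6.4.2 expectation does not mention O₂.

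D.6.4.2 gives no number for *few*, so nothing separates it from the significant correlations expected in D.6.4.1.

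**2. The plan's own figures.** The SBQ count in D.6.4 reproduces: 4 runs × 3 to 5 periods = 12 to 20. The correlations have no stated significance level, power or count. The only numerical threshold is in D.2.3: Z > 4.0, given as p < 10⁻⁷. This does not reproduce for a single test: 1 − Φ(4) = 3.2 × 10⁻⁵ one-sided, or 6.3 × 10⁻⁵ two-sided; 10⁻⁷ would need Z of about 5.2 one-sided.

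**3. What a non-significant correlation can show.** Assume two-sided 0.05 and one point per scan in the stated window, n = 6 + 4 = 10, treated as independent. The critical |r| is 0.632. By Fisher's z, power ≈ 1 − Φ(1.96 − atanh(r) × √(n − 3)).
- r = 0.3: about 13%.
- r = 0.5: atanh(0.5) × √7 = 0.549 × 2.646 = 1.453; 1 − Φ(0.507) = about 31%.
- r = 0.7: about 63%.
- r = 0.5 with the 4 + 4 window (n = 8): 0.549 × √5 = 1.228; 1 − Φ(0.732) = about 23%.

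If Z > 4.0 governed each correlation, power at r = 0.5 and n = 10 would be 1 − Φ(4 − 1.453) = about 0.5%.

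The range is wide in the other direction too. If a subject's 12 to 20 SBQ windows were pooled without averaging, there would be 120 to 200 points. Treated as independent, 120 points give 0.549 × √117 = 5.94 at r = 0.5, so power is close to 100%. Successive scans are not independent, however. In a simulation of 10-scan series, a lag-one autocorrelation of 0.5 raised the false-positive rate of a nominal 5% test to 9.0%.

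**4. Chance hits, for illustration.** Assume 0.05 per test, independence, no true association, and 4 to 8 areas. That number of areas is an Aim 1 expectation in D.5.4, carried over here.
- At least one CO₂ hit: 1 − 0.95⁴ = 18.5% to 1 − 0.95⁸ = 33.7%.
- Exactly one CO₂ hit, where the two statements of Hypothesis 4 disagree: 4 × 0.05 × 0.95³ = 17.1% to 8 × 0.05 × 0.95⁷ = 27.9%.
- At least one CO₂ hit if Z > 4.0 applied: 1 − (1 − 6.3 × 10⁻⁵)^m = 0.03% for m = 4 and 0.05% for m = 8.

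**5. Inputs the test depends on.** D.6.4 implies 18/6 = 12/4 = 3 s per scan, but D.2.1 gives a TR of 2.2 s, at which 6 scans last 13.2 s and 4 scans last 8.8 s. D.6.2.1 describes end-tidal CO₂ by nasal cannula; D.6.3 describes a transcutaneous measurement.

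**The case against.** The analysis-section bullets are worded as expectations, and naming CO₂ can be read as narrowing a general hypothesis. On that reading an O₂-only result is simply a failed prediction. This softens the Hypothesis 3 conflict but does not remove it, because the hypothesis text would still count that result as support. It does not help Hypothesis 4, where none and few are different outcomes.

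The other defences are sound as far as they go. The correlations are meant only to help separate the two explanations. Gas measures also enter the regressions as covariates (D.6.2.1, D.6.5), IBH controls for the cessation of breathing (D.6.2.2), and SBQ and IBH are compared by MANOVA (D.6.4.3). The hypotheses also predict the size of gas change, moderate against small. The study is exploratory.

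A reader might infer that multiplicity is uncontrolled and that chance alone is likely to confirm Hypothesis 3. The protocol does not support that. It states no significance level for these tests, D.2.3 is introduced as covering all data, and level and adjustment may sit in an analysis plan that is not at hand. D.2.3's steps do concern map clusters, and D.6.5.1 invokes them where D.6.4.1 and D.6.4.2 do not, so their reach is open. Running 40 to 80 per-subject tests (10 subjects × 4 to 8 areas) would make a chance hit very likely, but D.6.4 averages images within and then across subjects, so that scenario has less textual support. Nor would one isolated area plainly confirm Hypothesis 3, since D.6.4.3 expects non-specific activation in all areas during IBH.

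**Conclusion.** The point stands on the text. Hypothesis 3 and D.6.4.1 disagree on which gas must correlate, and Hypothesis 4 and D.6.4.2 disagree on whether any significant correlation is allowed. An analysis plan could add detail, but the protocol would still state each hypothesis in two ways.

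Reading few or no significant tests as absence of a gas effect is also unsound. The 31% power at r = 0.5 assumes 10 independent scans per correlation and two-sided 0.05. Pooling windows would change that figure greatly, but non-significance would still not establish absence without an interval. The 19% to 34% chance-hit range is hypothetical and becomes negligible under Z > 4.0, so it should not carry the argument. It would also be too strong to say that Aim 2 has no other protection against the respiratory confound. The change should be made, at modest priority.

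**What to change.** 1. Word each hypothesis identically in Section A, D.6.1 and D.6.4.1–D.6.4.2, and name CO₂ as the deciding gas.
2. For each subject, compute one correlation of CO₂ with mean grey-matter BOLD over the IBH windows and one over the SBQ windows, and convert each to Fisher z. Mean grey matter follows the plan's own expectation of a global breath-holding effect. The subject becomes the unit, so within-series autocorrelation no longer sets the p-value.
3. For Hypothesis 3, test the IBH values against zero across the 10 planned subjects at two-sided 0.05.
4. For Hypothesis 4, replace the none and few criteria with the paired SBQ-minus-IBH difference and the SBQ mean, each with a 95% confidence interval. An interval for the difference wholly below zero supports weaker coupling in SBQ. Do not conclude absence of a gas effect from non-significance. D.6.3 times the breath-holds to each subject's preceding SBQ pattern, which suits a paired comparison.
5. Treat O₂ and area-by-area correlations as descriptive.
6. Before using the test, reconcile the scan window (6 + 4 or 4 + 4), the scan interval (3 s or 2.2 s) and the CO₂ measure (end-tidal or transcutaneous).

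Cost: protocol wording plus the reconciliation in item 6, with no new data. Area-specific correlations no longer decide a hypothesis, and with 10 subjects the SBQ conclusion may be less definite. The CO₂ range in each condition should be reported alongside, because the smaller gas change that Hypothesis 4 predicts for SBQ can itself lower a correlation.
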